7.4 VARIABLES

7.4.1 EXPOSURES

Table 1 Market availability for the treatments of interest

Class	Drug	FDA approved*	FDA approved for stroke prevention in patients with non-valvular atrial fibrillation at risk for stroke
Direct thrombin inhibitors	Dabigatran	19 October 2010	19 October 2010
Direct Xa inhibitors	Rivaroxaban	1 July 2011	4 November 2011
	Apixaban	28 December 2012	28 December 2012

Table 1 (con't)

Market availability for the treatments of interest

Edoxaban	Phase III	N/A
Otamixaban	Phase III	N/A
Betrixaban	Phase II	N/A

*as of December2013

The primary contrast of interest is between new initiators of warfarin and new initiators of dabigatran, defined as no anticoagulation with *any oral anticoagulant* in the 12 months before the index prescription.

In the secondary analysis and as they become available for stroke prevention in NVAF patients, other NOAC medications will be compared to warfarin. The same definitions and inclusion/exclusion criteria will be applied.

Concomitant therapy with medications that are not cohort-defining medications (defined as simultaneous use on the day of dabigatran or warfarin initiation) will be accounted for in the study analyses as a covariate and used for balancing or stratification.

Study follow-up

We will follow patients for each of the outcomes of interest in a prospective manner and we will estimate measures of effect using person-time based analyses.

The primary analyses will use an 'as treated' approach. Follow-up will start the day after cohort inclusion, which is the day of treatment initiation, and will end at the time of disenrollment, end of the observation period (available data), death, admission to a nursing home, discontinuation of the index study exposure, or switch to a different anticoagulant whichever comes first. Exposure will be considered discontinued if there is a treatment gap ≥ 14 days from the end of calculated days supplied. Warfarin therapy involves dose titration following initiation before a stable therapeutic INR is obtained. We will use the reported days' supply as a proxy for duration of exposure following a dispensing as it may more adequately reflect the use pattern within a commercial health insurer database represented by UnitedHealth and MarketScan. This approach involves a potential mismatch between the presumed exposure derived from dispensing data and actual exposure. The utilization study (described in study protocol 1160.177) will inform the sensitivity analyses around this assumption and seek to clarify how sensitive results are to variations in the exposure assumption. Switchers will be censored in the as-treated approach on the day of the dispensing of the alternative medication. If switching was the consequence of a side effect of a drug, most likely the index drug was discontinued for some time before the new drug was initiated. Any clinical event therefore was most likely recorded during that period and will be

attributed to the index drug.

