0258T (transthoracic cardiac exposure for catheter-delivered aortic valve replacement; without cardiopulmonary bypass)
0259T (transthoracic cardiac exposure for catheter-delivered aortic valve replacement; with cardiopulmonary bypass)
0262T (implantation of catheter-delivered prosthetic pulmonary valve, endovascular approach)

at any time prior to and including the index date.

We will balance baseline covariates among patients initiating each drug by means of a multivariate confounder summary score (by matching on the exposure propensity score, with confounder balance assessed by the disease risk score). [\[R12-1912\]](#)

Cohort formation

We will receive new data as they become available on a periodic basis (every 6 months) and we will update the study cohorts through December 2015. Initiators of oral anticoagulants identified in each data cut, as previously described, will form sequential cohorts.

In each sequential cohort we will balance baseline covariates among patients initiating each drug by matching on the exposure propensity score and calendar quarter of initiation. Patients' follow-up will end when there is a treatment gap of ≥ 14 days from the end of calculated days supplied. Patients will be allowed to contribute only once.

[figure not shown]

Figure 1

Patient Selection Flow

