Hemorrhagic stroke	As primary ICD-9 discharge diagnosis (Dx): 431.x Intracerebral hemorrhage (ICH)	Median PPV 96% (86% if all discharge diagnoses) for ICH based on 2 validation studies [R14-0052]
Stroke uncertain classification	As primary ICD-9 discharge diagnosis (Dx): ICD-9 Dx code 436.x (acute, but ill-defined cerebrovascular disease)	Mini-Sentinel report: Median PPV of 81% for the code of 436 [R14-0052]
Transient Ischemic Attack (TIA)	ICD-9 Dx code 435.xx (transient cerebral ischemia) as the principal (primary) discharge diagnosis	PPV of 89% (primary Dx) and 77% (primary and secondary) in 1992 study [R13-0519] and 70% (primary only in Canadian database) [R13-0520] have been reported. Median PPV is 79% (72 if all discharge Dx) [R14-0052]
Myocardial infarction (MI)	ICD-9 Dx 410.X (acute myocardial infarction) excluding 410.x2 (subsequent episode of care), as the principal (primary) or the next (secondary) diagnosis AND a length of stay (LOS) between 3-180 days, or death if LOS is < 3 days	PPV 94% in Medicare claims data [R11-4316] PPV 88.4% in commercially-insured population [R11-4887]
Venous Thromboembolism (VTE)	DVT or PE (for codes see component outcomes below)	

Table 2 (con't) Outcome Definitions

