In addition, medication use in United Healthcare data and MarketScan data - as in all administrative healthcare databases - is restricted to prescription drug medication.

Consequently, the use of over-the-counter (OTC) medications (e.g., OTC aspirin) is not captured. In addition, exposure is assessed based on prescription pick-up at a pharmacy and might be misclassified in “as treated” analysis if patients do not take their medications. However, misclassification of prescription drug exposure is generally considered less than in other exposure assessment approaches, including physician prescribing records and patient self-reporting. [\[P13-03077\]](#) [\[P13-03078\]](#)

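### The 14-day gap rule gives no credit for inpatient days, so a hospital stay, alone or added to a late refill, can censor a patient who is still on treatment

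*Combined protocol and SAP*

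**What the plan says.** Section 7.4.1 (Study follow-up) makes as-treated follow-up primary and takes duration from the claim: "We will use the reported days' supply as a proxy for duration of exposure following a dispensing". It then sets the stopping rule: "Exposure will be considered discontinued if there is a treatment gap ≥ 14 days from the end of calculated days supplied". Section 7.3 (Cohort formation) repeats it: "Patients' follow-up will end when there is a treatment gap of ≥ 14 days from the end of calculated days supplied". Section 7.11 confirms the source of the exposure measure: "exposure is assessed based on prescription pick-up at a pharmacy". Drug supplied by a hospital is therefore outside it.

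Institutional care is handled in one respect. A nursing home stay excludes a patient at baseline (7.3) and ends follow-up later; 7.4.1 lists "death, admission to a nursing home, discontinuation of the index study exposure, or switch to a different anticoagulant whichever comes first". Hospital admission is not mentioned in either place.

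The plan recognises the general weakness: "This approach involves a potential mismatch between the presumed exposure derived from dispensing data and actual exposure". It also promises follow-up work: "The utilization study (described in study protocol 1160.177) will inform the sensitivity analyses around this assumption". Neither sentence refers to inpatient days. The available text does not define calculated days supplied, does not say whether unused supply carries forward, and does not say whether the censoring date is the end of supply or the end of the 14-day gap.

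**The concern.** A patient in hospital does not normally draw on the home supply, whether the anticoagulant is continued from hospital stock or held and resumed. The next refill is then due later by the length of the stay. A rule that counts calendar days from the end of nominal supply treats that delay as time off drug.

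Follow-up appears to be specific to each outcome: Table A4 lists the event among the reasons follow-up ends and is to be repeated for every outcome. A patient admitted for myocardial infarction or transient ischaemic attack should therefore stay in the stroke and major bleeding analyses. If the admission pushes the apparent gap to 14 days, the patient leaves those primary analyses because of an illness. Censoring that follows illness may be related to later risk, and Section 7.9.1 describes no adjustment for informative censoring.

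**Working it through.** **Inputs from the documents.** Gap threshold 14 days (7.3, 7.4.1). Exposure from pharmacy dispensings only (7.4.1, 7.11). Final person-time 24,100 years per group, with base rates of 31.59 (stroke) and 66.72 (major hemorrhage) per 1,000 person-years (Table 8).

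**Inputs assumed, because the documents do not give them.** Length of stay L; usual refill delay d, meaning refill date minus end of nominal supply; home supply unused during the stay and used afterwards; the stay falling before the refill.

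**Step 1: when the rule is triggered.** Apparent gap = d + L, so the label applies when L ≥ 14 − d.

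- d = 0: stay of 14 days or more
- d = 3: 11 days or more
- d = 7: 7 days or more
- d = 10: 4 days or more

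**Step 2: an example.** Assume a 30-day supply covering days 1–30, d = 7, and a stay on days 20–26.

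- Without the stay, the refill comes on day 37. The gap is 37 − 30 = 7 and the patient counts as persistent.
- With the stay, seven home days are saved and the refill comes on day 44. The gap is 44 − 30 = 14 and the patient counts as discontinued.
- With a credit of 7 days, supply ends on day 37. The gap is 44 − 37 = 7 and the patient counts as persistent.

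The censoring date is day 30 or day 44, depending on the unstated convention: 4 or 18 days after the last hospital day. Move the same stay to days 28–34 and day 30 falls inside it.

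**Step 3: how often a stay would trigger the label.** For lognormal stays with median m and log-SD 0.8, the share is 1 − Φ(ln((14 − d)/m)/0.8).

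| Median stay (days) | d = 0 | d = 3 | d = 7 | d = 10 |
|---|---|---|---|---|
| 3 | 2.7% | 5.2% | 14.5% | 36% |
| 5 | 9.9% | 16.2% | 33.7% | 61% |
| 8 | 24.2% | 34.5% | 56.6% | 80.7% |

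The refill delay drives much of this. If d is spread evenly over the whole days 0–13, stays of 3, 5 and 7 days trigger the label in 3/14 = 21%, 5/14 = 36% and 7/14 = 50% of patients. If d is spread over 0–6 days, the figure is 0% for all three, since 6 + 7 = 13. All of these are shares of stays or of hospitalised patients, not of the cohort.

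**Step 4: is it a power issue?** Solve r − 1 = (1.960 + 0.842) × √((1 + r)/E), where E is the expected number of warfarin events.

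- Stroke: E = 31.59 × 24.1 = 761, giving r = 1.149 (Table 8: 1.15).
- Major hemorrhage: E = 66.72 × 24.1 = 1,608, giving r = 1.101 (Table 8: 1.10).

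With 10% of person-time lost, these become 1.157 and 1.107. The effect on precision is negligible.

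**The case against.** The strongest reply is that the plan never says hospital days count as days off drug. A reader might infer such a rule, but the text is silent and its key term is undefined, so this is a gap in specification. That is fair. Still, a programmer given only this text would count calendar days, so the silence has a default.

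Four further points limit the claim.

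- A reader might infer that such a patient is censored without missing a dose. That does not follow. A refill 7 days late means uncovered days unless the recorded supply is wrong. What holds is that the plan's own rule accepts that delay as persistence, and the stay adds no further non-use of home supply.
- A reader might infer that the rule removes patients in the high-risk weeks after discharge. The documents do not support this, because the censoring date is unstated and could fall during the stay or, for a stay that begins after nominal supply ends, before it.
- A reader might infer a bias between arms. The rule is identical in both, and nothing in the documents shows that admissions for other reasons differ by arm. Section 7.4.1 links warfarin titration to uncertain exposure duration, so refill delays might differ, but direction and size are unknown.
- An admission for stroke or major bleeding during follow-up is itself the event. Only later events, after an admission for something else, are at issue.

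It may also be covered elsewhere. The general mismatch is acknowledged and sensitivity analyses are promised, and the text refers to a further analysis section that is not in the available document. A provision there cannot be ruled out.

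Finally, a credit assumes treatment resumes after discharge. Where it was stopped for good, the credit adds unexposed time. This stands, and it is why the credit needs a cap and a comparison without it.

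**Conclusion.** The concern holds in limited form. As the available text stands, inpatient days deplete supply that was not used at home, and any stay with d + L of at least 14 days can turn a persisting patient into a discontinued one. Short stays with prompt refills are unaffected. Under the assumed lengths of stay and refill delays, between 2.7% and 81% of stays would reach the threshold. That range mainly shows that the documents cannot settle the size. The proportion of the cohort involved, and any effect on the dabigatran–warfarin comparison, cannot be calculated from them.

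What is at stake is illness-related censoring and exposure misclassification in the primary as-treated analysis, not power. The general caveat and the unspecified sensitivity analyses do not tell the analyst what to do with hospital days. This is a cheap improvement worth making; it does not show that the planned results would be biased.

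**What to change.** In Sections 7.3 and 7.4.1:

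1. State that days spent as a hospital inpatient are added to the end of the current days' supply, and so are not counted in the 14-day gap, identically in both arms.
2. Set in advance a maximum number of days credited per stay. The documents give no basis for a particular value. A cap matters because the myocardial infarction definition in Table 2 admits long stays: "a length of stay (LOS) between 3-180 days, or death if LOS is < 3 days".
3. State whether the censoring date is the end of supply or the end of the 14-day gap.
4. Report the analysis without the credit as a sensitivity analysis.

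Leave the other censoring rules unchanged.

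The cost is a few sentences and a small programming step. Length of stay is already needed for the infarction definition, so the data should be to hand. The downside is that where the drug was stopped for good in hospital, up to the credited number of unexposed days will count as exposed. The cap limits this, and the uncredited analysis shows whether it matters.

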7.4.2 OUTCOME(S)

The primary outcomes of interest include stroke (hemorrhagic, ischemic, uncertain classification) and major bleeding. Secondary outcomes are: stroke or systemic embolism, , transient ischemic attack (TIA), myocardial infarction (MI), venous thromboembolism (VTE), deep vein thrombosis (DVT), pulmonary embolism (PE).

Systemic embolism (defined as an acute vascular occlusion of the extremities or any organ, such as kidneys, mesenteric arteries, spleen, retina or grafts), ischemic stroke, hemorrhagic stroke, stroke of uncertain classifications, major intracranial bleeding, major extracranial bleeding, major gastrointestinal (GI) bleeding, major upper GI bleeding, major lower GI bleeding, major urogenital bleeding, major other bleeding. Further outcomes include hepatotoxicity and all-cause mortality.

As mortality data in the commercial databases is currently limited to inpatient deaths, we will seek to improve the ascertainment of the death outcome through external linkage, such as with the Social Security Death Master File.

Table 2 **Outcome Definitions**

Outcome	Hospital Discharge Code(s)	Comments
Primary Outcomes		
Stroke	As primary ICD-9 discharge diagnosis (Dx): 431.x Intracerebral hemorrhage (ICH) 433.x1 Occlusion and stenosis of precerebral arteries with cerebral infarction 434.x1 Occlusion and stenosis of cerebral arteries with cerebral infarction 436.x Acute, but ill-defined cerebrovascular events	See Mini-Sentinel report for PPV for individual codes or other algorithms [R14-0052]
Major hemorrhage	Major intracranial bleeding, major extracranial bleed (for codes see component outcomes below)	
Secondary outcomes		
Stroke or systemic embolism	Stroke or systemic embolism (for codes see component outcomes below)	

Table 2 (con't)

Outcome Definitions

Outcome	Hospital Discharge Code(s)	Comments
Systemic embolism	ICD-9 Diagnoses: 444.x Arterial embolism	No validation studies available. Codes are thought to be specific because of the substantial clinical symptomatic and required therapy.

Table 2 (con't) Outcome Definitions

Ischemic stroke	As primary ICD-9 discharge diagnosis (Dx): ICD-9 Dx 433.x1 Occlusion and stenosis of precerebral arteries with cerebral infarction ICD-9 Dx 434.x1 Occlusion and stenosis of cerebral arteries with cerebral infarction	PPV 95.5% in commercially-insured population for the codes in any position [R11-4887] Use of codes in the primary position generally increases the PPVs [R14-0052]
Hemorrhagic stroke	As primary ICD-9 discharge diagnosis (Dx): 431.x Intracerebral hemorrhage (ICH)	Median PPV 96% (86% if all discharge diagnoses) for ICH based on 2 validation studies [R14-0052]
Stroke uncertain classification	As primary ICD-9 discharge diagnosis (Dx): ICD-9 Dx code 436.x (acute, but ill-defined cerebrovascular disease)	Mini-Sentinel report: Median PPV of 81% for the code of 436 [R14-0052]
Transient Ischemic Attack (TIA)	ICD-9 Dx code 435.xx (transient cerebral ischemia) as the principal (primary) discharge diagnosis	PPV of 89% (primary Dx) and 77% (primary and secondary) in 1992 study [R13-0519] and 70% (primary only in Canadian database) [R13-0520] have been reported. Median PPV is 79% (72 if all discharge Dx) [R14-0052]
Myocardial infarction (MI)	ICD-9 Dx 410.X (acute myocardial infarction) excluding 410.x2 (subsequent episode of care), as the principal (primary) or the next (secondary) diagnosis AND a length of stay (LOS) between 3-180 days, or death if LOS is < 3 days	PPV 94% in Medicare claims data [R11-4316] PPV 88.4% in commercially-insured population [R11-4887]
Venous Thromboembolism (VTE)	DVT or PE (for codes see component outcomes below)	

Table 2 (con't) Outcome Definitions

Deep vein thrombosis (DVT)	
Validated algorithm:
 
ICD-9 451.1x (Phlebitis and thrombophlebitis of deep vessels of lower extremities)
 
ICD-9 451.2x (of lower extremities, unspecified)
 
ICD-9 451.81 (of Iliac vein)
 
ICD-9 451.9x (of unspecified site)
 
ICD-9 453.1x (thrombophlebitis migrans)
 
ICD-9 453.2x (venous embolism and thrombosis of vena cava)
 
ICD-9 453.8x (venous embolism and thrombosis of other specified veins)
 
ICD-9 453.9x (venous embolism and thrombosis of unspecified site)
 
Not in the validated algorithm but will be included following Mini-Sentinel recommendation for VTE outcome:
 
ICD-9 453.40 (Venous embolism and thrombosis of unspecified deep vessels of lower extremity (includes DVT)
 
ICD-9 453.41 (Venous embolism and thrombosis of deep vessels of proximal lower extremity (includes femoral, iliac, popliteal, thigh, and upper leg)
 
ICD-9 453.42 (Venous embolism and thrombosis of deep vessels of distal lower extremity (includes calf, lower leg, peroneal, and tibia)
 
ICD-9 453.0 (Hepatic vein thrombosis)
	
Algorithm for Deep vein thrombosis (DVT): ICD-9 codes of 451.1, 451.2, 451.81, 451.9, 453.1, 453.2, 453.8, 453.9 [hospital discharge, any position] had PPV of 0.72 and specificity > 0.99 in Medicare population [R11-4334]
 
Mini-Sentinel: while using ICD-9 codes 415.x (PE), 451.x and 453.x (DVT) as a VTE event yielded the highest PPV, for a specific event (DVT or PE) PPV was lower; therefore, the performance of algorithms depends on a population studied [R13-0522]

Pulmonary Embolism (PE)	ICD-9 415.1x (pulmonary embolism and infarction)	PPV of 72% in a community sample (45 YO and older) [R05-0358]
Major intracranial bleeding	
ICD-9 diagnosis:
 
430.x (Subarachnoid hemorrhage (SAH))
 
431.x (Intracerebral hemorrhage (ICH))
 
432.x (other and unspecified intracranial hemorrhage, including 432.1x – subdural hemorrhage)
	PPV 77% or higher reported [R14-0052]
Major extracranial bleeding	Major upper GI bleed, major lower and unspecified GI bleed, major urogenital bleed, major other bleed (for codes see component outcomes below)	No validation studies available for this outcome
Major GI bleeding	Major upper GI bleeding, major lower/unspecified GI bleeding (for codes see component outcomes below)	No validation studies available for this outcome

Table 2 (con't) Outcome Definitions

Major upper GI bleed	
ICD-9 diagnoses:
 
531.0x (acute gastric ulcer with hemorrhage with/without obstruction)
 
531.2x (with hemorrhage and perforation with/without obstruction)
 
531.4x (chronic or unspecified gastric ulcer with hemorrhage with/without obstruction)
 
531.6x (with hemorrhage and perforation with/without obstruction)
 
532.0x (acute duodenal ulcer with hemorrhage with/without obstruction)
 
532.2x (with hemorrhage and perforation with/without obstruction)
 
532.4x (chronic or unspecified duodenal ulcer with hemorrhage with/without obstruction)
 
532.6x (with hemorrhage and perforation with/without obstruction)
 
533.0x (acute peptic ulcer of unspecified site with hemorrhage with/without obstruction)
 
533.2x (with hemorrhage and perforation with/without obstruction)
 
533.4x (chronic or unspecified peptic ulcer of unspecified site with hemorrhage with/without obstruction)
 
533.6x (with hemorrhage and perforation with/without obstruction),
 
534.0x (acute gastrojejunal ulcer with hemorrhage with/without obstruction)
 
534.2x (with hemorrhage and perforation with/without obstruction)
 
534.4x (chronic or unspecified gastrojejunal ulcer with hemorrhage with/without obstruction)
 
534.6x (with hemorrhage and perforation with/without obstruction)
 
578.0 (hematemesis) OR
 
ICD-9 procedure code 44.43 (endoscopic control of gastric or duodenal bleeding) OR
 
CPT code 43255 (upper gastrointestinal endoscopy including esophagus, stomach, and either the duodenum and/or jejunum as appropriate with control of bleeding, any method)
	PPV of 87.8% in commercially-insured population [R11-4887]
Major lower GI bleeding	
Lower GI/unspecified GI site bleeds [R11-2274]:
 
Diverticulosis of small intestine with hemorrhage: 562.02
 
Diverticulitis of small intestine with hemorrhage: 562.03
 
Diverticulosis of colon with hemorrhage: 562.12
 
Diverticulitis of colon with hemorrhage: 562.13
 
Hemorrhage of rectum and anus: 569.3x
 
Angiodysplasia of intestine with hemorrhage: 569.85
 
Blood in stool: 578.1x
 
Hemorrhage of GI tract, unspecified: 578.9
	
PPVs for individual codes [R11-2274]:
 
562.12 – 91.7%
 
562.13 – 66.7%
 
569.3 - 71.4%
 
569.85 – 100%
 
578.1 - 81.8%
 
578.9 -88.2%

Table 2 (con't) Outcome Definitions

Major urogenital bleed	ICD-9 diagnoses: Hematuria: ICD-9 Dx: 599.7 Excessive/frequent menstruation: ICD-9 Dx 626.2x and secondary diagnosis indicating acute bleeding: anemia (280.0, 285.1, 285.9), [R11-2274]	PPVs for individual codes [R11-2274] : 599.7 - 75.0% 626.2 – 100% (2 cases) [R11-2274]
Other major bleeds	Other major bleeds [R11-2274] : Hemathrosis: 719.1x Hemopericardium: 423.0x Hemoptysis: 786.3x Epistaxis: 784.7x Hemorrhage not specified 459.0x Acute posthemorrhagic anemia 285.1x	PPVs for individual codes [R11-2274] : 719.1x – 100% 786.3x – 80% 784.7x – 100% 459.0x – 100% 285.1x – 100%

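### The secondary outcome named major lower GI bleeding is coded as lower plus unspecified site, so some upper GI bleeds can enter the lower GI result

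*Combined protocol and SAP*

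**What the plan says.** - **Outcome list, Section 7.4.2.** The bleeding outcomes are given as "major gastrointestinal (GI) bleeding, major upper GI bleeding, major lower GI bleeding, major urogenital bleeding, major other bleeding". Upper and lower appear as two sites, and unspecified site is not mentioned.
- **Table 2, row for major lower GI bleeding.** The row label matches the outcome list, but the code list beneath it is headed "Lower GI/unspecified GI site bleeds". Six entries name a lower source (562.02, 562.03, 562.12, 562.13, 569.3x, 569.85). The other two are "Blood in stool: 578.1x" and "Hemorrhage of GI tract, unspecified: 578.9".
- **Table 2, row for major upper GI bleed.** It holds the hemorrhage codes within 531 to 534, then "578.0 (hematemesis) OR", then "ICD-9 procedure code 44.43 (endoscopic control of gastric or duodenal bleeding) OR", then CPT 43255. Because the parts are joined by OR, either procedure code is enough on its own.
- **Table 2, composite rows.** Major GI bleeding names its second component as lower/unspecified, and major extracranial bleeding names it as lower and unspecified.
- **Annex, Table A3.** The results table is produced again for each outcome. The text available gives no rule for attributing a stay that meets both the upper and the lower definition.

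**The concern.** A reader of the reports will take a hazard ratio headed major lower GI bleeding as an estimate for the lower tract. As coded, it is an estimate for the lower tract plus every bleed recorded under 578.1x or 578.9, some of which may be upper. The clearest case is a stay with 578.9 and procedure 44.43. The procedure places the bleed in the stomach or duodenum and the plan's upper definition is met, yet the stay also counts as lower.

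If the dabigatran effect differs between the upper and lower tract, the lower GI result becomes a mixture of the two effects, and the contrast between sites is blurred. The label would be carried through six interim reports and a final report (Section 4). The plan already treats the same problem differently for stroke. Code 436.x is neither ischemic nor hemorrhagic; it has its own row as stroke of uncertain classification and still counts in overall stroke.

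**Working it through.** **1. The plan's nearest figure.** Table 8 has no line for upper or lower GI bleeding, only for major GI bleeding as a whole. Inputs from Table 8 and Section 7.9.1: base rate 31.63 per 1,000 person-years, 10,000 to 24,100 person-years per group, 1:1 matching, two-sided alpha 0.05, power 80%. With E = 0.03163 × person-years, solve

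log RR = (1.960 + 0.842) × sqrt(1/E + 1/(E × RR)).

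For the final report E = 762, and 2.802 × sqrt(1/762.3 + 1/(762.3 × 1.149)) = 2.802 × 0.0495 = 0.139 = log 1.149. The seven computed values are 1.236, 1.211, 1.193, 1.178, 1.167, 1.157 and 1.149. Table 8 states 1.24, 1.21, 1.19, 1.18, 1.17, 1.16 and 1.15, so all agree on rounding. This line pools both code lists, so splitting the lower row does not change it.

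**2. The code lists side by side.** The upper and lower lists share no code. Applying the two Table 2 rows as written:

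| Codes on the stay | Meets upper | Meets lower |
|---|---|---|
| 531.4x only | yes | no |
| 562.12 only | no | yes |
| 578.9 only, true site upper | no | yes |
| 578.9 with 44.43 or CPT 43255 | yes | yes |
| 531.4x with 578.1x | yes | yes |
| 531.4x with 562.12 | yes | yes |

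The last line is proper: both sites are coded. Lines three to five are the problem.

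**3. Composites.** Major GI bleeding is the union of the two lists. Major extracranial bleeding and major hemorrhage contain that union. A stay in any line of the table counts in all three, whichever site it is given.

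**4. What mixing would do.** Let f be the share of warfarin-group events in the lower row that are truly upper. If recording of site does not depend on treatment, the expected ratio is

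RR_row = (1 − f) × RR_lower + f × RR_upper,

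so the shift from RR_lower is f × (RR_upper − RR_lower). The documents give neither f nor the two RRs; every value below is an assumption. Take 40% to 70% of the row's events as coming from 578.1x or 578.9, and 30% to 60% of those as upper. Then f runs from 0.4 × 0.3 = 0.12 to 0.7 × 0.6 = 0.42.

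| RR_lower | RR_upper | RR_row at f = 0.12 | RR_row at f = 0.42 |
|---|---|---|---|
| 1.30 | 0.80 | 1.144 + 0.096 = 1.24 | 0.754 + 0.336 = 1.09 |
| 0.80 | 1.30 | 0.704 + 0.156 = 0.86 | 0.464 + 0.546 = 1.01 |
| 1.50 | 1.00 | 1.32 + 0.12 = 1.44 | 0.87 + 0.42 = 1.29 |
| any value | same value | no shift | no shift |

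The direction and size depend wholly on the assumed pair of RRs.

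**The case against.** The strongest reply is that nothing is hidden. Three places in Table 2 say that unspecified site is included: the row's own sub-heading and two composite rows. The row also follows a cited case definition for serious bleeding, with positive predictive values of 81.8% for 578.1 and 88.2% for 578.9. Read as lower/unspecified, the estimate is interpretable. This stands, and it rules out calling the row a concealed coding error. It does not cure the name used in the outcome list and the row label, and no predictive value for site is given.

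Three stronger readings are tempting, and the documents do not support them.

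- **Upper GI bleeds in general are counted as lower.** They are not. The lists share no code, so an upper bleed enters only if it is recorded under, or also carries, 578.1x or 578.9.
- **Counting one patient under both outcomes is itself an error.** Outcomes overlap by design elsewhere: 431.x is in both stroke and major intracranial bleeding. Nothing shown says that upper and lower are exclusive, and a patient with true bleeds at both sites should count in both.
- **The bias has been shown to be material.** It has not. The shares and the RRs in the working are all assumed.

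The public text also cites sections that it does not contain (6.4.3 and 6.9.2), so an attribution rule may exist there. The code list in Table 2 would still need to agree with it.

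**Conclusion.** The point holds in a limited form. The outcome's name promises a lower site, its code list delivers lower plus unspecified, and the rows as written count some stays as lower GI events although they meet the plan's own upper definition. The consequence is confined to reading the site-specific results: the lower GI result may be mixed, and the upper result misses upper bleeds recorded only as unspecified. Major GI bleeding, major extracranial bleeding and the primary major hemorrhage outcome do not change.

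The size cannot be estimated from the documents. There is no mixing bias if the upper and lower effects are equal. Under the assumed shares of 12% to 42%, the shift is 0.12 to 0.42 times the difference between the two RRs. That shows what could happen, not what will.

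**What to change.** 1. Label the existing outcome major lower/unspecified GI bleeding in Section 7.4.2, the Table 2 row and the results tables, and keep reporting it.
2. Add two rows to Table 2: site-specific lower GI bleeding (562.02, 562.03, 562.12, 562.13, 569.3x, 569.85) and GI bleeding of unspecified site (578.1x, 578.9). This matches the handling of stroke of uncertain classification.
3. State an attribution rule. A stay with 578.1x or 578.9 that also meets any part of the upper definition (531 to 534 hemorrhage codes, 578.0, procedure 44.43 or CPT 43255), and has no site-specific lower code, counts as upper only. Limiting the rule to the two procedure codes would leave a stay coded 531.4x with 578.1x in both.
4. Leave major GI bleeding and the wider composites as they are; no code leaves them.

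The cost is two more rows, a short rule, and fewer events with a wider interval in the site-specific lower row. If 40% to 70% of the present row's events rest on unspecified codes alone (an assumption), 60% to 30% remain. The interval on the log scale would then be about 1/sqrt(0.6) = 1.29 to 1/sqrt(0.3) = 1.83 times as wide. Keeping the lower/unspecified result beside it limits that loss. The primary outcomes and Table 8 need no change.
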